11.2.1 Investigator Responsibilities

The Principal Investigator of an investigational site is responsible for ensuring that the study is conducted in accordance with the Clinical Study Agreement, the clinical investigation plan, ICH GCP, ISO 14155, ethical principles that have their origins in the Declaration of Helsinki, any conditions of approval imposed by the reviewing IRB/EC, and prevailing local and/or country laws and/or regulations, whichever affords the greater protection to the patient.

The Principal Investigator's responsibilities include, but are not limited to, the following.

- Prior to beginning the study, sign the Clinical Study Agreement and comply with the Investigator responsibilities as described in such Agreement.
- Prior to beginning the study, sign Protocol Signature page documenting their agreement to conduct the study in accordance with the protocol.
- Provide their qualifications and experience to assume responsibility for the proper conduct of the study and that of key members of the site team through up-to-date curriculum vitae or other relevant documentation and disclose potential conflicts of interest, including financial, that may interfere with the conduct of the clinical study or interpretation of results.
- Make no changes to or deviate from this protocol, except to protect the life and physical well-being of a patient in an emergency; document and explain any deviation from the approved protocol that occurred during the course of the clinical investigation.
- Create and maintain source documents throughout the clinical study and ensure their availability with direct access during monitoring visits or audits; ensure that all clinical-investigation-related records are retained per requirements.
- Ensure the accuracy, completeness, legibility, and timeliness of the data reported to the Sponsor in the eCRFs and in all required reports.
- Record, report, and assess (seriousness and relationship to the Varithena, ETA device, and procedure) every AE as applicable per the protocol.
- Report to the IRB/EC and regulatory authorities any SUSARs, if required by applicable laws or regulations or this protocol or by the IRB/EC and supply the Sponsor with any additional requested information related to the safety reporting of a particular event.
- Allow the Sponsor to perform monitoring and auditing activities and be accessible to the clinical research monitor or auditor and respond to questions during monitoring visits or audit(s).
- Allow and support regulatory authorities and the IRB/EC when performing auditing activities.
- Ensure that informed consent is obtained in accordance with applicable laws, this protocol and local IRB/EC requirements.
- Provide adequate medical care to a patient during and after a patient's participation in a clinical study in the case of adverse events, as described in the Informed Consent Form (ICF).

Owner(s): [name]

Vault: BSC Quality - NAT-rel

Title: VERITAS Study Protocol

Document #/Version: BSC-00887/ver. 1.2

- Inform the patient of the nature and possible cause of any adverse events experienced.
- Inform the patient of any new significant findings occurring during the clinical investigation, including the need for additional medical care that may be required.
- Provide the patient with well-defined procedures for possible emergency situations related to the clinical study and make the necessary arrangements for emergency treatment.
- Ensure that clinical medical records are clearly marked to indicate that the patient is enrolled in this clinical study.
- Ensure that, if appropriate, patients enrolled in the clinical investigation are provided with some means of showing their participation in the clinical investigation, together with identification and compliance information for concomitant treatment measures (contact address and telephone numbers shall be provided).
- Inform, with the patient's approval or when required by national regulations, the patient's personal physician about the patient's participation in the clinical investigation.
- Make all reasonable efforts to ascertain the reason(s) for a patient's premature withdrawal from clinical investigation while fully respecting the patient's rights.
- Ensure that an adequate investigation site team and facilities exist and are maintained and documented during the clinical investigation.

11.2.2 Investigator CV

The Investigator will provide the Sponsor or designee with his/her, as well as those of any sub-Investigator or staff personnel with significant study responsibilities, current curriculum vitae (CV) and any revisions/updates.

11.2.3 Investigator Agreement Form (Form FDA 1572)

The Investigator will be required to sign and date an Investigator Agreement form provided by the Sponsor for the original and each subsequent change in Investigator at the site and return the original signed document to the Sponsor. A copy of the signed form will be given to the Investigator for their files.

11.2.4 Financial Agreements and Financial Disclosure

Financial agreements with each site are described separately.

Financial disclosure statements will be completed for the Investigator and all sub-investigators to disclose potential conflicts of interest (per 21 CF Part 54 and ISO 14155). The Investigator is responsible for ensuring completed and signed financial disclosure forms are submitted to the Sponsor or designee. A copy of the form(s) will be given to the Investigator for their files. Financial disclosure information will be collected by the Sponsor before the start of the study and maintained for one year after study completion.

11.2.5 Site Qualifications

The Institution must have appropriately qualified Investigators, and clinical and administrative support staff in place to adequately conduct the trials according to GCP in general and must have the adequate expertise and staff to conduct this study in compliance with the relevant guidelines and regulations (see section 11.1) and to treat incompetent great saphenous vein with the study treatments.

Owner(s): [name]

11.3 Institutional Review Board (IRB)/Independent Ethics Committees (IEC)

11.3.1 Institutional Approval of the Protocol

It is the responsibility of the Investigator to submit this protocol, the ICF (approved by the Sponsor or designee), relevant supporting information and all types of patient recruitment information to the IEC/IRB for review and approval prior to site initiation. A copy of the written approval of the protocol and ICF must be received by the Sponsor or designee prior to recruitment of patients. Prior to implementing changes in the study, the Sponsor and IEC/IRB must also approve any revised informed consent documents and amendments to the protocol with documentation of the approvals submitted to the Sponsor or designee. The approval document should clearly state the study reference, date of review and actions taken.

The Investigator will be responsible for keeping the IEC/IRB apprised of the progress of the study, any changes to the protocol, deviations from the protocol and serious/unexpected adverse events.

11.3.2 Ethics/IRB Committee Membership Roster

The Investigator must submit a complete and current roster of the IEC/IRB to the Sponsor or designee. Some institutions, due to reasons of confidentiality, may not release their roster. Where such instance occurs, an Institutional signed and dated Statement of Compliance identifying the institution's Federal Wide Assurance Number, assigned by the Office of Human Research Protection within the Department of Health and Human Services, is an acceptable substitute.

11.4 Patient Privacy and Confidentiality

The confidentiality of records that may be able to identify patients and/or the Sites and Investigators will be protected in accordance with applicable laws, regulations and guidelines and HIPAA requirements.

The Sponsor and Investigator affirm and uphold the principle for the patient's right to protection against invasion of privacy. Throughout this study, all data collected and analysed by the Sponsor (data controller) or designee (data processor) will be treated confidentially and identified by an identification number.

To verify compliance with the protocol, the Sponsor will require the Investigator to permit its designee access to the patient's primary medical record to review those portions that directly concern this study (including but not limited to laboratory test results, radiology images, and hospital and outpatient records).

As part of required content of the informed consent, the patient must be informed that his/her records will be reviewed by the Sponsor, Sponsor representative and/or a representative of the appropriate regulatory agency, if applicable. The informed consent or related document will also state that patient privacy will be maintained pursuant to the Health Insurance Portability and Accountability Act (HIPAA), 21 CFR 21. Should access to such medical records require a waiver or authorization separate from the statement of informed consent, the Investigator will obtain such permission in writing from the patient before the patient is entered in the study.

Data collected during this study may be used to support the development, registration or marketing of Varithena. Collected data may be reviewed by the Sponsor and/or its representatives, independent auditors who validate the data on behalf of the Sponsor, third parties with whom the Sponsor may develop, register or market Varithena, national or local regulatory authorities and the IRB/EC which granted approval for this study to proceed. Data may be transferred to and used for the purpose (s) for which it was originally collected in, other countries which may not afford the same level of protection that applies within the countries where this study is conducted. The Sponsor, as the data controller, will ensure that, prior any

Vault: BSC Quality - NAT-rel

Title: VERITAS Study Protocol

Document #/Version: BSC-00887/ver. 1.2

transfer, appropriate safeguards are in place to protect the data as required under the General Data Protection Regulation (EU) 2016/679 and other applicable data protection legislation.

11.5 Study Monitoring

Monitoring type (Remote, Onsite) and frequency during the conduct of the study will be detailed in the study monitoring plan and will be performed by qualified personnel from the Sponsor or Sponsor designee. During the monitoring visit, the progress of the study will be discussed with the Investigator or his/her representative. The ICF will be reviewed for signatures and the eCRFs checked for completeness and accuracy. Patient source data must be available for review. The Investigator and his/her staff are expected to cooperate with the study monitor and be available during at least a portion of the monitoring visit to review the eCRFs and any queries/resolutions, answer questions, and provide any missing information.

The study monitor will record the date of each visit together with a summary report outlining the status and progress of the study. Proposed actions will be discussed with the Investigator or delegate study team members and confirmed in writing.

Telephone and electronic mail contact will be made with the Investigator and study staff as necessary during the data collection and report writing periods. All relevant study communications will be filed in the investigator site file.

11.6 Modification of the Protocol

All amendments to the protocol must be documented in writing, reviewed, and approved by the Investigator and Sponsor and submitted to the IEC/IRB for approval/positive vote prior to initiation. If the protocol amendment substantially alters the study design or potential risk to the patient, new written informed consent must be obtained from each patient for continued participation in the study.

11.7 Suspension or Termination of Study

If conditions arise requiring further clarification before the decision can be reached to proceed with or terminate the study, the study will be suspended until the situation has been resolved.

The Sponsor has the right to terminate this study and remove all study material from the site at any time. Examples of situations where this might occur include:

- It becomes apparent that patient enrollment is unsatisfactory with respect to quality and/or quantity or data recording is chronically inaccurate and/or incomplete.
- The incidence and/or severity of adverse events in the study indicate a potential health hazard caused by the study treatment.

11.8 Trial Completion

The study will be considered complete with regard to the primary endpoint after all patients have completed the 3-month follow up visit, were discontinued prior to the 3-month follow up visit, have died, or the follow up visit window is closed.

For regulatory purposes the end of the study with regard to all follow up after all patients have completed the 36-month follow up visit, were discontinued prior to the 36-month follow up visit, have died, or the follow up visit window is closed at which point the declaration of the end of study will be submitted to the IEC/IRB, as required.

Following this, the Sponsor or delegate will advise the sites on the procedure for closing the study.

Owner(s): [name]

Vault: BSC Quality - NAT-rel

Title: VERITAS Study Protocol

Document #/Version: BSC-00887/ver. 1.2

Once the end of the study has been declared, no more prospective patient data will be collected and sites must co-operate with any data queries regarding existing data to allow for analysis and publication of results.

11.9 Clinical Study Report

Irrespective of the outcome of the study the Sponsor will prepare a Clinical Study Report (CSR) within one year of completion of the study or within three months of early suspension or termination of the study.

11.10 Departure from Protocol

No departure may be made from the protocol unless an amendment has been agreed to in writing by both the Investigator and the Sponsor and approved by the IEC/IRB.

No waivers will be granted for inclusion and exclusion criteria to this protocol.

11.10.1 Protocol Deviations

All protocol deviations will be listed and will be assessed as major or minor throughout the clinical study and finalised prior to database lock.

Criteria for protocol deviations will be defined and reviewed prior to database lock and described in the Protocol Deviation Management Plan. The following protocol deviations will be considered:

- Violation of exclusion or inclusion criteria
- Non-compliance to treatment (major deviations from the planned schedule of administration)
- Continuously missed evaluations of efficacy variables or major deviations in the timing of efficacy related assessments

11.11 Recording, Access to and Retention of Source Data

Investigators are required to prepare and maintain adequate source documentation which includes:

- Documents relative to the patient medical history that verify eligibility criteria
- Records covering patient participation in the study including basic identification information, results of physical examinations and diagnostic tests, original laboratory results (initialled and dated by Investigator), therapy, study treatment administration, concurrent medication information, pathology reports, and visit/consult notes.

All key data must be recorded in the patient's source documents including the informed consent acquisition.

The Investigator must permit authorized representatives of the Sponsor, the regulatory authorities, the IEC/IRB, and auditors to inspect facilities and records relevant to the study.

The monitor (auditors, IEC/IRB or regulatory inspectors) may check the eCRF entries against the source documents. The consent form will include a statement by which the patients allow the above-named access to source data that substantiate information recorded in the eCRFs. These personnel, bound by professional secrecy, will not disclose any personal information or personal medical information.

As described in the ICH GCP Guidelines, 'essential documents', including eCRFs, source documents, consent forms, laboratory test results, etc., should be retained by the Investigator until at least two years after the last approval of a marketing application in an ICH region or at least two years have elapsed since the formal discontinuation of a clinical development of the IP. These documents may be retained for a longer period however if required by the applicable regulatory requirements or by an agreement with the Owner(s): **[name]**

Sponsor. The Investigator must obtain written permission from the Sponsor prior to destruction of any study documents.

These records must be made available at reasonable times for inspection and duplication, if required, by a properly authorized representative of FDA in accordance with 21 CFR 312, 21 CFR 812, or other regulatory authorities in accordance with regulatory requirements.

11.12 Electronic Case Report Forms

The Investigator is responsible for maintaining adequate and accurate source documents from which accurate information will be transcribed in to eCRFs that have been designed to capture all observations and other data pertinent to the clinical investigation. eCRFs should be completed by the Investigator or delegate as stated on the Delegation of Authority Log. Overwriting of information or use of liquid correcting fluid is not allowed in source documentation.

Once the study monitor has verified the contents of the completed eCRF against the source data, queries may be raised if the data are unclear or contradictory. The eCRFs must be reviewed and electronically signed and dated by the Investigator once all data has been entered and all queries resolved.

11.13 Publications

All manuscripts, abstracts or other modes of presentation arising from the results of the study must be reviewed and approved in writing by the Sponsor, in advance of submission. The review is intended to protect Sponsor proprietary information existing either at the date of commencement of the study or generated during the study. No individual Investigator may publish results from his/her site until after publication of the primary manuscript describing the full study population.

The detailed obligations regarding the publication of any data, material results or other information that is generated or created in relation to the study shall be set out in the agreement between the Investigator and Sponsor.

In accordance with recommendations from the International Committee of Medical Journal Editors, the study will be listed in a publicly accessible registry of clinical trials such as clinicaltrials.gov.

11.14 Audit/Inspections

To ensure compliance with relevant regulations, data generated by this study must be available for inspection upon request by representatives of the FDA, the Sponsor and its representatives, and the IEC/IRB for each study site.

The VVSymQ is a 5-item PRO that includes the following five symptoms: heaviness, achiness, swelling, throbbing, and itching. Two versions of the VVSymQ were created to reflect pre-treatment and post-treatment. Table 1 shows the Pre-Treatment VVSymQ items, response options, and response option scores. Table 2 shows the Post-Treatment VVSymQ items, response options, and response option scores. The only difference between the versions is that the reference to the “leg to be treated” in the pre-treatment version is replaced with “treated leg” in the post-treatment version. Response options and scores remain the same in both versions.

Table 3: Pre-Treatment VVSymQ

Item	Response Scale	Response Option Scores
Please answer the following for the time since waking up today...	N/A	N/A
Since waking up today, how often had you had the following problem in your leg to be treated? Heaviness	None of the Time A Little of the Time Some of the Time A Good Bit of the Time Most of the Time All of the Time	0 1 2 3 4 5
Since waking up today, how often had you had the following problem in your leg to be treated? Achiness	None of the Time A Little of the Time Some of the Time A Good Bit of the Time Most of the Time All of the Time	0 1 2 3 4 5
Since waking up today, how often had you had the following problem in your leg to be treated? Swelling	None of the Time A Little of the Time Some of the Time A Good Bit of the Time Most of the Time All of the Time	0 1 2 3 4 5
Since waking up today, how often had you had the following problem in your leg to be treated? Throbbing	None of the Time A Little of the Time Some of the Time A Good Bit of the Time Most of the Time All of the Time	0 1 2 3 4 5
Since waking up today, how often had you had the following problem in your leg to be treated? Itching	None of the Time A Little of the Time Some of the Time A Good Bit of the Time Most of the Time All of the Time	0 1 2 3 4 5

Owner(s): [name]

Table 4: Post-Treatment VVSymQ

Item	Response Scale	Response Option Scores
Please answer the following for the time since waking up today...	N/A	N/A
Since waking up today, how often had you had the following problem in your treated leg? Heaviness	None of the Time A Little of the Time Some of the Time A Good Bit of the Time Most of the Time All of the Time	0 1 2 3 4 5
Since waking up today, how often had you had the following problem in your treated leg? Achiness	None of the Time A Little of the Time Some of the Time A Good Bit of the Time Most of the Time All of the Time	0 1 2 3 4 5
Since waking up today, how often had you had the following problem in your treated leg? Swelling	None of the Time A Little of the Time Some of the Time A Good Bit of the Time Most of the Time All of the Time	0 1 2 3 4 5
Since waking up today, how often had you had the following problem in your treated leg? Throbbing	None of the Time A Little of the Time Some of the Time A Good Bit of the Time Most of the Time All of the Time	0 1 2 3 4 5
Since waking up today, how often had you had the following problem in your treated leg? Itching	None of the Time A Little of the Time Some of the Time A Good Bit of the Time Most of the Time All of the Time	0 1 2 3 4 5

MedDRA	Medical Dictionary for Regulatory Activities
PP	Per-Protocol
PT	Preferred Term
RFA	Radiofrequency ablation
SADR	Serious Adverse Drug Reaction
SAE	Serious Adverse Event
SAP	Statistical Analysis Plan
SOC	System Organ Class
TLF	Tables, Listings and Figures
USPI	United States Prescribing Information

1 INTRODUCTION

The SAP is based on protocol version 1.2 dated 17Aug2023 and the electronic case report form (eCRF) version 4.0 dated 13Jul2023. On April 1st, 2024, Boston Scientific made the decision to terminate enrollment and follow-up in this study. The termination was not related to adverse event signals. Due to early termination the primary and secondary endpoints per protocol will not be performed. However, some observational tables and listings will be created for reporting requirement purposes only. This plan will therefore only include analysis to be performed for the abbreviated Clinical Study Report (CSR) and ClinicalTrials.gov.

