4.1 Study Objective

This study will collect comparative evidence on patient reported outcomes of Varithena compared to ETA when used to treat the incompetent Great Saphenous Vein (GSV). ETA will include either Radiofrequency ablation or endovenous laser ablation according to the site's standard practice. This study will provide long term (1-year, 2-year, and 3-year) outcomes.

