4.4 Primary Endpoint

The primary endpoint will assess the change in Varicose Veins Symptoms Questionnaire (VVSymQ) between baseline and 3-month post treatment.

Owner(s): [name]

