9.4.2 Primary Efficacy Endpoint Analysis

The absolute change in VVSymQ score between baseline and 3-month follow-up will be evaluated for each subject. Changes in scores will be summarized by treatment group (n, mean, standard deviation, min, max, and 95% confidence interval (CI)). The study is not powered to test formal statistical hypotheses, however results of a t-test comparing mean absolute change between treatment groups will be presented.

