3.1 Safety Analyses

Adverse Events

Adverse Drug Reaction (ADR) / Serious Adverse Drug Reaction (SADR) related to Varithena were documented from the start of the index procedure through the latest completed visit prior to study termination, the latest subject visit being the 12-month visit at the time of termination. In addition, only SAE related to ETA or to the procedure were to be documented from the start of index procedure through the original planned 36-month follow up timeframe.

Adverse events were coded according to Medical Dictionary for Regulatory Activities (MedDRA) the current version and will be reported by system organ class (SOC) and preferred term (PT). The MedDRA version used for reporting the study will be the version used for coding the trial and will be specified in the clinical study report and as a footnote in the related outputs.

The Investigator or physician sub-Investigator determined the seriousness of each AE and whether it is Varithena, ETA, or procedure related.

The following summaries will be provided by treatment and total:

- Overall summary of AEs
- All AEs by primary SOC and PT
- AEs suspected to be related to procedure and/or device by primary SOC and PT
- AEs by primary SOC, PT and worst severity
- AEs leading to study discontinuation
- Most frequent AEs ($\geq 5\%$) by primary SOC and PT

AEs will be summarized by presenting the number and percentage of patients having at least one AE, having at least one AE in each primary SOC and for each PT. A patient with multiple occurrences of an AE will be counted only once in the category.

There were no SAEs reported at the time of study termination.

Partial dates will be imputed using the rules defined in [Appendix 7.1](#).

All AEs reported in the database will be listed with the SOC, PT, and investigator's Verbatim terms.

Deaths

There were no patient deaths reported at the time of study termination.

GENERAL STATISTICAL METHODS

The statistical analyses will be performed on the analysis datasets with appropriate software, SAS® Software version 9.4 (SAS Institute, Cary, N.C.).

Continuous data will be summarized with means, medians, standard deviations, quartiles (25th and 75th) minima and maxima, unless otherwise specified. Categorical data will be summarized with observed counts and percentages for each category. Unless otherwise specified, the percentage denominator will be the number of patients in the analysis population.

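### Early termination alone does not justify specifying no VVSymQ output, because the protocol's primary analysis is a by-arm summary with a nominal t-test that remains valid at a smaller n

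*SAP*

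**What the plan says.** Protocol 4.1 gives the objective: "This study will collect comparative evidence on patient reported outcomes of Varithena compared to ETA". It adds a long-term part: "This study will provide long term (1-year, 2-year, and 3-year) outcomes". Protocol 4.4 defines the endpoint: "The primary endpoint will assess the change in Varicose Veins Symptoms Questionnaire (VVSymQ) between baseline and 3-month post treatment".

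Protocol 9.4.2 plans n, mean, standard deviation, minimum, maximum and 95% confidence interval of the change by treatment group, and says that a t-test between groups will also be presented. It qualifies that test: "The study is not powered to test formal statistical hypotheses". Protocol 9.1 likewise states that there is no pre-specified between-group hypothesis and that the study is not powered for a difference. It gives 2.0 points as the minimally detectable difference for about 100 patients.

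SAP section 1, written after the sponsor ended enrollment and follow-up, says: "Due to early termination the primary and secondary endpoints per protocol will not be performed". What remains is limited: "some observational tables and listings will be created for reporting requirement purposes only". On why the trial stopped, it says only: "The termination was not related to adverse event signals".

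The outputs that the SAP names are adverse events, disposition, demographics, medical history, protocol deviations and manometer tubing use in the Varithena arm. VVSymQ appears only in the visit schedule (SAP 2.3). SAP 2 reports 43 patients randomised and 40 treated, 21 of them with Varithena. On follow-up, SAP 3.1 gives "the latest subject visit being the 12-month visit at the time of termination".

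**The concern.** Early termination would be a good reason to drop an analysis that depends on reaching its planned size, such as a powered hypothesis test. The protocol planned no such analysis. A mean change with its interval can be computed from whatever patients have both assessments, and the interval itself shows how little or how much they tell.

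The objective is comparative patient-reported outcomes. Protocol 3.3 motivates the trial by noting that earlier Varithena trials were against placebo. If no patient-reported output is specified, the report will describe who was treated and which adverse events were recorded, but will give no result on the question for which patients were randomised. VVSymQ was scheduled at screening, 7 days and 3 months, so the 3-month time point lay within the follow-up that at least one patient completed.

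The SAP also keeps what such a table would need: a baseline definition, visit windows and a rule for choosing between assessments in one window (SAP 3.4).

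**Working it through.** **Inputs.** Planned size about 100 in a 1:1 ratio, standard deviation 5.0 in both arms, two-sided alpha 0.05, detectable difference 2.0 (Protocol 9.1). Treated: 40, of whom 21 received Varithena (SAP 2), so 40 − 21 = 19 received ETA. The number with 3-month VVSymQ is in neither document, so it is varied below.

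**Step 1: reproduce the plan's figure.** The smallest observed difference that is significant in a two-sample t-test with 50 per arm is

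t(0.975; 98) × 5.0 × √(1/50 + 1/50) = 1.98,

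which matches the stated 2.0. Power at a true difference of 2.0 is then about 51%. The figure is a significance threshold, equal to the planned 95% interval half-width. It is not a difference detectable with 80% power, which would be 2.83 points with 50 per arm. This agrees with the protocol's own statement that it is not powered, so no power target was lost when enrollment stopped.

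**Step 2: does any step fail at a smaller n?** Protocol 9.4.2 needs a change score per patient, then a mean, standard deviation, range and interval per arm, then a t-test. None requires 100 patients. Protocol 11.8 already treats the primary endpoint stage as complete when some patients stop before 3 months.

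**Step 3: precision within arm, if all 40 are evaluable.**
- Varithena: t(0.975; 20) × 5.0/√21 = 2.28
- ETA: t(0.975; 18) × 5.0/√19 = 2.41
- Planned, n = 50: t(0.975; 49) × 5.0/√50 = 1.42

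**Step 4: precision between arms.** Half-width = t(0.975; n1 + n2 − 2) × SD × √(1/n1 + 1/n2).

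| Evaluable at 3 months | SD | Half-width (points) |
|---|---|---|
| 50 + 50 (planned) | 5.0 | 1.98 |
| 21 + 19 (all treated) | 5.0 | 3.20 |
| 21 + 19 | 4.0 | 2.56 |
| 21 + 19 | 6.0 | 3.85 |
| 16 + 14 (assumed) | 5.0 | 3.75 |
| 11 + 9 (assumed) | 5.0 | 4.72 |

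With 21 and 19, power at a true difference of 2.0 points is about 23%.

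**Step 5: what the intervals could show.** Protocol 3.3 cites changes of −4.87 and −5.06 for 1% Varithena. If this arm improved by the same amounts, the n = 21 intervals for the improvement would be 4.87 ± 2.28 = 2.6 to 7.1 and 5.06 ± 2.28 = 2.8 to 7.3. This is an illustration only: the cited values are week-8 electronic diary scores, not this trial's 3-month questionnaire.

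**The case against.** The strongest reply is that the data are too few to be useful. Even in the best case the between-arm half-width of 3.2 exceeds the 2.0-point design figure. It also exceeds the whole gap between 1% Varithena and placebo in the cited trials (4.87 − 2.13 = 2.74 and 5.06 − 2.00 = 3.06). A within-arm interval that excludes zero says little about treatment effect when placebo patients improved by about 2 points, and it says nothing about ETA. All of this stands. It is a reason to label the result imprecise, not a reason to specify no result.

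The reply can add that the omission is open: the SAP announces it, applies it to all efficacy endpoints and calls the report abbreviated. That also stands, and it limits what can be inferred. Several stronger readings are tempting, but the documents do not support them:

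- **That the omission is result-driven or selective.** Nothing shows that the choice depended on the data.
- **That 3-month data exist for most patients.** The 12-month visit is the latest visit reached, perhaps by one patient. Enrollment and follow-up ended together, so recently treated patients may never have reached month 3.
- **That the planned analysis was purely descriptive.** The protocol synopsis and 9.4.2 also plan a two-sample t-test, though without a formal hypothesis.
- **That VVSymQ certainly will not be reported, or that the trial reports nothing.** The list in SAP 4.4 is open-ended, and adverse events are still summarised by treatment.
- **That the ETA arm is dropped altogether.** The sentence in SAP 4.4.1.4 sits under study treatment and concerns procedure data.
- **That the SAP removed the 2- and 3-year outcomes.** Termination did.

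**Conclusion.** The point holds in this form: the only reason given does not support specifying no VVSymQ output, and as specified the SAP gives no result on the comparative patient-reported objective. An open-ended list does not replace a specified primary summary.

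The cost of the smaller sample is precision. The between-arm half-width rises from 1.98 points as planned to 3.20 if all 40 treated patients are evaluable, and to 3.75 or 4.72 under the two smaller assumed counts. The comparison would be imprecise in every case.

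These figures rest on three assumptions. The standard deviation of 5.0 comes from baseline values in earlier trials, not from change scores; a range of 4 to 6 gives 2.6 to 3.9 with all 40. The ETA count is by subtraction and reflects treatment received, because allocation of the 43 randomised patients is not given. The 3-month counts below 40 are illustrative. The actual number could be lower still, and it is the first figure that the sponsor should state.

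**What to change.** Replace the SAP section 1 sentence that drops the endpoints with a commitment along these lines:

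> VVSymQ at baseline, 3 months and other available visits, and the change from baseline to 3 months, will be summarised by arm (n, mean, SD, minimum, maximum, 95% CI), with the number evaluable at month 3 in each arm. The unadjusted between-arm difference in mean change will be given with its 95% CI and labelled descriptive and imprecise.

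The unadjusted difference follows the protocol's planned comparison. Any estimate adjusted for baseline VVSymQ should be marked supplementary.

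Three details need to be settled with it:

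- **Analysis set.** SAP 3.2 defines only As Treated. Name the set as treated patients by randomised arm, state any difference from treatment received, and account for the 43 − 40 = 3 patients randomised but not treated, who were not followed (Protocol 7.3.10).
- **Missing scores.** Protocol 9.4.1 defers this to the SAP, and SAP 3.5 covers only counts and dates. State that the change uses patients with both assessments.
- **Other scales.** Add a VVSymQ listing, and present rVCSS, VEINES-QOL/Sym and EQ-5D in the same format.

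The cost is a few tables from data collected under the visit schedule, and an imprecise estimate that must be labelled as such. If the sponsor still omits the analysis, the SAP should give the month-3 count per arm and a reason other than termination itself.
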